Date of protocol: 10/14/2020

IRB Approval Date: 11/24/2020

Version of protocol: 7

IND number: 139015

Institutional protocol number: OSU 17102

DLT definition	

• Acute GVHD <math>\geq</math> Grade 3

• Any non-hematologic toxicity <math>\geq</math> Grade 3 related to Daratumumab

• Hematologic toxicity: grade 4 toxicity not related to the underlying disease and not responding to growth factor or transfusion within 7 days

• Grade 3 or higher non-neurologic immune-related adverse events (e.g. diarrhea, pruritus, rash) that responds to corticosteroids and improve to grade 1 or less within 4 weeks will NOT count as DLTs. Optional biopsy of affected organs will be encouraged to help determine whether the immune-related condition is due to GVHD

Enrollment schedule	
Dose level 1: Weekly Dara for eight doses; if no infusional toxicity observed or GVHD observed, proceed to next dose level. 3 patients at a time can be enrolled in one dose level.
 
If no GVHD is observed after at least 2 weeks after DLI, enrollment will proceed to next dose level.

Definitions for safety-evaluability	Received at least one dose of Daratumumab
Definition for DLT evaluability	
All patients are evaluable for DLT except patients who are unable to receive 3 doses of daratumumab in dose level 1, or 3 doses of daratumumab and DLT for dose levels 2 and 3 due to progression of AML.
 
DLT observation period will be from the first dose of daratumumab till 7 days post 3rd dose of daratumumab (for dose level 1) and from the first dose of daratumumab till at least 4 weeks post DLI (for dose level 2 and 3)

Definitions for efficacy evaluability:	All eligible patients who receive at least one dose of Daratumumab, do not withdraw consent, and are evaluated for response at week 8.
Dose-limiting toxicity:	Grade 3 or 4 GVHD
Special situations	

1. If patients attain response before DLI, there will be three options at the discretion of treating physician :

a. Proceed with DLI

Date of protocol: 10/14/2020

IRB Approval Date: 11/24/2020

Version of protocol: 7

IND number: 139015

Institutional protocol number: OSU 17102

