	

b. Continue Daratumumab maintenance( If Daratumumab is given as maintenance, a schedule of 16mg/kg every 2 weeks for 16 (8 doses) weeks and then monthly for 6 months will be administered)

c. Proceed with second transplant.

 
2. If patients develop steroid-responsive GVHD and remission before DLI, there will be two options at the discretion of treating physician :
 

a. Continue Daratumumab maintenance (If Daratumumab is given as maintenance, a schedule of 16mg/kg every 2 weeks for 16 weeks (8 doses) and then monthly for 6 months will be administered)

b. Proceed with second transplant.

--	---

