If a patient in dose level 1 receives less than 3 doses of Daratumumab due to reasons other than toxicity, then this patient will not be evaluable for DLT and will be replaced. An additional patient will be added to the dose cohort. For dose level 2 or 3, if a patient does not receive 3 doses of Daratumumab and DLI due to reasons other than toxicity, then this patient will not be evaluable and will be replaced. There will be no intrapatient dose escalation. Phase I may involve as few as 3 patients (three at the starting dose level if  $\geq 2$  DLTs are experienced) and a maximum of 18 patients will be treated, six at each of the 3 dose levels. We assume that 10% of the patients in this group will not be evaluable due to not finishing the DLT observation period. So we expect to accrue a minimum of 4 patients and a maximum of 20 patients.

At OSU, 125 patients with AML/MDS underwent allo-HSCT in 2012 and 2013. Among these, 32 patients relapsed. About 40% were from related donor and 60% from unrelated donor. So we expect to accrue approximately 6 patients for the related sibling donor cohort and 10 patients for the unrelated donor cohort per year. Hence, the minimum study duration for phase I would be about 8-10 months and the maximum study duration would be around 2.5-3.5 years (accounting for the DLT observation period) for related sibling donors and unrelated donors respectively.

After the MTD has been established, we will expand to Phase II trial. For phase II part, considering that patients receiving transplant from related sibling donor or unrelated donor with each treated at the corresponding MTD of Daratumumab plus DLI are expected to have similar profiles for response and toxicities, we will combine these 2 cohorts together in phase II stage. The null hypothesis is that combination of Daratumumab and DLI has a response rate of < 10% in patients with relapsed AML following allo-HSCT. The alternative hypothesis is that Daratumumab has a response rate of at least 30% in patients with relapsed AML following allo-HSCT. With a type 1 error (alpha): 0.05, and a type 2 error (beta = 1 – power): 0.20, the sample size would be 25 patients for Phase II. If the number of patients achieving ORR is 6 or more, then we reject the null hypothesis. We would include 3-6 patients from

Date of protocol: 10/14/2020

IRB Approval Date: 11/24/2020

Version of protocol: 7

IND number: 139015

Institutional protocol number: OSU 17102

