### 16.2 Analysis methods:

Analysis datasets:

Efficacy sets: All evaluable patients will be included in the analysis of the primary endpoint. The term evaluable is defined as any eligible patient who receives at least one dose of Daratumumab, does not withdraw consent, and is evaluated for response week 8; patients who fail to have a week-8 assessment due to early progression, death or toxicity will also be considered evaluable for response and categorized as non-responders. Patients who fail to have a week-8 assessment for other reasons (e.g., refusal due to travel constraints) will be considered unevaluable and will not be included in the denominator when calculating ORR rate.

Safety sets: The safety analysis dataset will include all eligible patients who receive one dose of daratumumab.

The adverse events will be examined and worst grade adverse events will be recorded for each patient and summarized by type, severity, and attribution (if possible) using NCI CTCAE version 4 criteria. Tolerability of the regimen will be assessed by summarizing the number of patients who require dose modifications and/or dose delays. In addition, we will also capture the proportion of patients who go off treatment due to adverse events or even those who refuse further treatment for lesser toxicities that inhibit their willingness to continue participation on the trial. All patients who have received at least one dose of daratumumab will be evaluable for toxicity and tolerability.

The primary endpoint of phase II is to evaluate overall response rates (ORR) to the combination of Daratumumab and DLI. The ORR will be defined as complete remission (CR), complete remission with incomplete marrow recovery (CRi), partial remission (PR) and morphological leukemia free

Date of protocol: 10/14/2020

IRB Approval Date: 11/24/2020

Version of protocol: 7

IND number: 139015

Institutional protocol number: OSU 17102

state (MLFS). The proportion of patients achieving ORR among efficacy sets will be calculated and 95% confidence interval will be estimated. In addition, the ORR among patients who received at least 3 doses of Daratumumab and DLI will be calculated as well. The ORR rate among MRD positive patients and patients with overt morphological relapse will be estimated as well. The MRD conversion rate from MRD positive to MRD negative, and the 3-month GVHD rate (both grade II-IV and III-IV) will be similarly analyzed.

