Demographical and clinical characteristics of study patients will be described using mean and standard deviation, median and range, or frequency and percent depending on the data type and distribution. Overall survival (OS) will be defined as the time from the first treatment of Daratumumab to death or last contact date if no death. Progression free survival (PFS) will be defined as the time from the first treatment of Daratumumab to the date of progression or death or last clinical assessment date if no progression or death. Kaplan-Meier curves will be generated to estimate OS/PFS at 6 months. The association between patient characteristics and OS/PFS will be evaluated in univariable Cox proportional hazard regression model.

To examine the rate of GVHD (both grade II-IV and III-IV), the event will be onset of GVHD and time to GVHD will be defined as the period of time from first treatment of Daratumumab to the onset of GVHD. Death and early relapse without GVHD will be competing risks. Cumulative incidence rate of GVHD at 3-month with 95% confidence intervals will be estimated from the cumulative incidence curves. Competing risk regression analysis will be conducted to estimate the association between patient characteristics and GVHD.

For pre/post-treatment comparisons in the correlative part of the study, a paired t-test will be applied. Two-tailed p values <0.05 will be considered statistically significant in all analyses.

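### The plan has no rule for counting a response before DLI that is followed by a second transplant; if week 8 is then missed, the responder drops out of the primary ORR

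*Combined protocol and SAP*

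**What the plan says.** **Pathway.** The synopsis (section 2, Special situations) states: "If patients attain response before DLI, there will be three options at the discretion of treating physician". The third option is "Proceed with second transplant". The same option is one of two open to a patient with steroid-responsive GVHD and remission before DLI. Neither entry gives a date for the transplant or says how response is to be assessed afterwards.

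**Analysis set.** The synopsis requires an efficacy-evaluable patient to have been evaluated for response at week 8. Section 16.2 adds that a patient without that assessment because of early progression, death or toxicity is evaluable and counts as a non-responder. For everyone else it says: "Patients who fail to have a week-8 assessment for other reasons (e.g., refusal due to travel constraints) will be considered unevaluable". Those patients are left out of the ORR denominator. Second transplant is named in neither group.

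**Objective and assessments.** The phase II primary objective (section 5.1) is response by week 8. Marrow is scheduled at screening, before DLI and at the end of study (section 12.2). The study logistics in the synopsis place the middle one after dose 3 and before dose 4.

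**The concern.** The protocol creates a route by which a patient who has responded may leave the planned treatment sequence because of that response, and the primary analysis does not provide for it. Section 16.2 illustrates its exclusion with travel constraints, a reason plausibly unrelated to outcome. Transplant after response is the opposite case: the patient would be missing because the treatment worked. Applied as written, the rule would remove successes and never failures along this route.

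What is at stake is the phase II decision. It rests on a count of at least 6 responders among 25 patients, so one or two uncounted responders can change it. If the question is settled only once such a patient exists, it will be settled with the outcome known.

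**Working it through.** **Inputs from section 16.** The null hypothesis is that the combination "has a response rate of < 10% in patients with relapsed AML following allo-HSCT", so p0 = 0.10. The alternative is p1 = 0.30. The error rates and size are given as "With a type 1 error (alpha): 0.05" and a type 2 error of "0.20, the sample size would be 25 patients for Phase II". The null is rejected with 6 or more responders.

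**Assumed input.** q is the share of true responders who go to second transplant and have no week-8 assessment. The documents give no value, so q = 10%, 20% and 30% are shown.

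**Step 1: reproduce the stated design.** With X ~ Bin(25, p):
- P(X ≥ 6 | p = 0.10) = 0.0334
- P(X ≥ 6 | p = 0.30) = 0.8065

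The stated design reproduces as a one-sided exact test at 0.05. Section 16.2 says "Two-tailed p values <0.05 will be considered statistically significant in all analyses", but 0.0334 exceeds 0.025, so the six-responder rule is a one-sided rule.

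**Step 2: the boundary.** Take 25 treated patients.
- 6 responders, 1 dropped: 5/24 = 20.8%, rule not met. If counted, 6/25 = 24.0%, rule met.
- 7 responders, 2 dropped: 5/23 = 21.7%, not met. If counted, 7/25 = 28.0%, met.
- 8 responders, 3 dropped: 5/22 = 22.7%, not met. If counted, 8/25 = 32.0%, met.

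Recomputing the exact test on the smaller denominator does not rescue the first case: P(X ≥ 5 | n = 24, p = 0.10) = 0.085. At a true ORR of 30%, the chance of exactly 6 responders in 25, where one loss reverses the decision, is C(25,6) × 0.3^6 × 0.7^19 = 14.7%.

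**Step 3: power at a true ORR of 30%.**

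(a) 25 treated, dropped patients not replaced. Each patient is a counted responder with probability 0.30 × (1 − q), and power is P(X ≥ 6) for n = 25.

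(b) Dropped patients replaced until 25 are evaluable. The response rate among evaluable patients is 0.30(1 − q) / (1 − 0.30q), for example 0.27/0.97 = 27.8% at q = 10%.

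| q | Expected responders lost of 7.5 | Expected ORR among evaluable | Power (a) | Power (b) |
|---|---|---|---|---|
| 0 | 0 | 30.0% | 80.7% | 80.7% |
| 10% | 0.75 | 27.8% | 70.4% | 73.6% |
| 20% | 1.5 | 25.5% | 57.7% | 64.5% |
| 30% | 2.25 | 23.1% | 43.2% | 53.4% |

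The plan does not say whether unevaluable phase II patients are replaced, so both columns are needed. In (a), resetting the cut-off to the exact 0.05 level for the evaluable number changes little: 70.5%, 58.0% and 44.6%.

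**Step 4: type I error.** Under (a) at p0 = 0.10, P(X ≥ 6) with success probability 0.10(1 − q) falls from 0.033 to 0.021, 0.012 and 0.007. The error therefore runs against the treatment.

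**Step 5: week-8 marrow taken after transplant.** The patient then stays in the denominator. The option is open only to patients already judged to be in response or remission, and ORR already includes CR, CRi, PR and MLFS. A remission seen after transplant usually leaves the responder status unchanged. It changes the endpoint only where the response was lost, or improved across the ORR threshold, between the pre-DLI marrow and week 8.

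**The case against.** A reader might infer that every patient who goes to second transplant lacks a week-8 assessment, so that the plan certainly discards these responders. The documents do not say so. The synopsis lists a marrow after week 8, the calendar in section 12.1.3 places it on days 57 to 71, and section 12.2 lists an end-of-study marrow, none with an exemption for transplanted patients. Section 12.4 does not list second transplant as completing the study, and the transplant date is open. The loss is therefore conditional on a missed assessment.

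The by-week-8 wording of the objective can also be read as crediting a response on the pre-DLI marrow. That is a fair reading, but the evaluable set in section 16.2 does not carry it through, so the two remain unreconciled.

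A reader might further infer that the plan generally credits transplant remissions to daratumumab plus DLI. Step 5 shows why that reaches only a narrow set of patients.

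On size, the 10% to 30% shares have no source in the documents. To be lost, a patient must respond before DLI, be sent to transplant rather than to DLI or maintenance, and miss week 8. Section 4.1 says that only a small number of relapsed patients are eligible for a second transplant. That sentence concerns all relapsed patients rather than responders, but it makes the 30% row a stress case.

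What stands is that no rule covers this pathway, and that the literal rule removes a responder whenever week 8 is missed because of transplant.

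**Conclusion.** The point holds in conditional form. The plan offers a second transplant to early responders without saying how their response counts, and where the week-8 assessment is missed for that reason, section 16.2 as written excludes a responder because of the outcome. ORR is then biased downward. The risk is a missed signal, not a false claim of efficacy, since type I error falls as well.

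One such patient is enough to reverse the decision at six responders. Beyond that, the size rests on the assumed share q, on a true ORR of 30%, and on whether dropped patients are replaced: power falls from 80.7% to between 70.4% and 43.2% without replacement, or to between 73.6% and 53.4% with it, as q goes from 10% to 30%. The documents do not show which value of q is realistic, and it may be small. The change is still worth making before outcomes are known.

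**What to change.** In section 16.2:
- Define the primary ORR as best response (CR, CRi, PR or MLFS) documented by week 8 and before any second transplant or other anti-leukaemic therapy.
- State that patients who go to second transplant stay in the denominator, and that a response first seen after transplant does not count.
- Add a sensitivity analysis counting responders transplanted before week 8 as non-responders.
- Bring the efficacy-evaluability definition in the synopsis into line.

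With early responders counted this way, the design keeps its own figures: type I error 0.033 and power 80.7% with 25 patients.

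The cost is a few sentences of analysis text. The pre-DLI marrow is already scheduled, the response form in the appendix records the assessment date, and patient management is unchanged. The downside is small: a pre-DLI response reflects daratumumab alone and may be unconfirmed at week 8. The ORR already planned among patients who received at least 3 doses of daratumumab and DLI addresses the attribution question.

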## 4 INTRODUCTION

### 4.1 AML RELAPSE POST-TRANSPLANT

Acute myeloid leukemia (AML) is a molecularly heterogeneous disease with significant genetic complexity. Allogeneic hematopoietic cell transplantation (Allo-HCT) has curative potential and most patients with intermediate or adverse risk molecular and cytogenetic subtypes will proceed to allogeneic HCT in first complete remission. With increasing availability of donor sources and reduced-intensity conditioning, number of transplants is expected to increase. However, AML relapse incidence post Allo-HCT varies between 18-47% based on the conditioning regimen. Relapse after Allo-HCT has a dismal prognosis, with a median post-relapse overall survival (OS) of 3-6 months. According to historical cohorts, if not transplanted for a second time, such patients have a 6-month median OS of only about 10%. For example, chemotherapy and donor lymphocyte infusion provided discouraging post-relapse median OS of 51 and 84 days, respectively in a large recent study. Although second Allo-HSCT may offer durable remissions, only a small number of patients after relapse are eligible to receive a second transplant. In a recent CIBMTR analysis of 1788 patients relapsing after allogeneic HSCT, 3-year overall survival was 4% for patients relapsing within 1-6 months after an allograft and 12% for patients who relapsed in the 6-24 months after an allograft. Currently, there is no standard or satisfactory treatment available for this group of patients. We propose here a Phase I/II study to determine the activity and safety of Daratumumab in patients post Allo-HCT with relapsed AML and myelodysplastic syndrome (MDS) transformed to AML.

### 4.2 ROLE OF DLI

Recent studies have shown T-cell exhaustion in post-transplant relapses and that it can be reversed during effective human antileukemic responses to donor lymphocyte infusion (DLI). There is increasing evidence that T cell infiltration at site of malignancy is critical to disease control. In a group of chronic myeloid leukemia patients who traditionally have the highest responses to DLI (about 85%), Bachireddy et al found that baseline T cell content in marrow and subsequent increase in T cell content following DLI were higher in responders versus non-responders. Recent guidelines note recommended doses of DLI for related and unrelated donors. In the halo setting with post-transplant cyclophosphamide, Donor lymphocyte infusion with doses up to  $1 \times 10^6$ /kg were noted to have remission rates of up to 30% in patients with AML.

### 4.3 PRECLINICAL DATA REGARDING DARATUMUMAB

Daratumumab is a first-in-class anti-CD38 monoclonal antibody approved for treatment of refractory multiple myeloma; encouraging responses with an acceptable safety profile were seen in heavily pre-treated patients. Daratumumab has been shown to also have immunomodulatory effects on T cell subsets; increased T cell numbers (CD8+ cells) in both peripheral blood and bone marrow were observed following Daratumumab treatment. Responders had higher numbers of CD8+ t cells than non-responders, which was most pronounced after Cycle 3. A highly immunosuppressive subset of T-regs expressing CD38 decreased significantly following Daratumumab treatment.

Date of protocol: 10/14/2020

IRB Approval Date: 11/24/2020

Version of protocol: 7

IND number: 139015

[figure not shown]
Institutional protocol number: OSU 17102

In addition to the T cell effects, we have discovered that CD38 antibody-binding to AML cells can encourage cell-to-cell killing or fratricide. This is consistent with the fact that AML cells (both primary and cell lines) express Fc gamma Receptors much like fully differentiated monocytes and macrophages, and are capable of antibody-mediated destruction of target cells albeit at a lower efficiency. Below, we provide data attesting this hypothesis.

[figure not shown]
**Methods:** Primary patient samples were obtained from apheresis when patients presented with high white blood cell counts and required leukapheresis. AML cell lines MOLM-13, THP-1, OCI-AML3 and MV4-11 were also used. Commercial anti-CD38 antibodies were used for these experiments.

Results:

**I. *IFN- $\gamma$  promotes an activated M1 phenotype in AML cells.*** Myeloid cells within the context of tumors commonly display M2-like characteristics, which serves to promote tumor growth and survival. Here, we tested whether treatment with IFN- $\gamma$  could skew AML cells toward an M1 phenotype. We treated the AML cell lines MOLM-13, MV4-11, OCI-AML3 and THP-1 overnight with or without IFN- $\gamma$  and measured expression of the M1 markers CD80 and CD86. Results showed that overnight treatment with IFN- $\gamma$  significantly increased the expression in all 4 cell lines of both CD80 and CD86 (data not shown). We also verified increased surface expression of CD86 via flow cytometry (data not shown). Next, we treated samples from AML patients overnight with versus without IFN- $\gamma$  and measured the expression of these markers. Results showed that transcripts for both CD80 (Figure 1) and CD86 (data not shown) were significantly increased.

[figure not shown]

**II. *IFN-γ increases FcγRI expression and phagocytic ability in AML cells.*** It has previously been shown that IFN-γ could increase the expression of FcγR1 in AML cells which led to the investigation of IFN-γ treatment combined with drug-conjugated anti-FcγRI antibody as a potential therapy for AML. Here, we explored the possibility that IFN-γ treatment would not only increase FcγRI but would also enhance the phagocytic ability of these AML cells, as FcγRI is a major effector of phagocytosis in myeloid cells. For this, we first treated the AML cell lines MOLM-13, MV4-11, OCI-AML3 and THP-1 overnight with or without IFN-γ and measured FcγRI expression by qPCR and flow cytometry. Results showed that, as expected, IFN-γ significantly increased both the transcript (Figure 2A) and surface expression (Figure 2B) of FcγRI. Next, we treated the cell lines overnight as above, and then subjected them to a phagocytosis assay using antibody-opsonized sheep red blood cells as targets. As shown in Figure 2C, IFN-γ treatment significantly enhanced the phagocytic ability of MOLM-13 and THP-1, with MV4-11 and OCI-AML3 showing a trend toward enhancement. We then tested the effects of IFN-γ on patient samples and found that it significantly increased FcγRI expression (Figure 2D). These results indicate that IFN-γ can enhance not only the expression, but also the function, of FcγR in AML cells.

**III. *IFN-γ increases CD38 expression in AML cells.*** Internalization of therapeutic antibodies by the tumor cells is beneficial within the context of antibody-drug conjugates, but such internalization also reduces the ability of immune effector cells to bind and destroy the targets. CD38 is currently being investigated as an antigen that shows less internalization than CD33, thereby potentially serving as a superior target for effector cell-mediated ADCC. Hence, we measured the expression of CD38 on these cells. To do this we treated the AML cell lines MOLM-13, MV4-11, OCI-AML3 and THP-1 overnight with or without IFN-γ and then measured levels of CD38. Results showed that IFN-γ treatment led to a significant increase in CD38 in all cell lines tested, as measured by qPCR (Figure 3A) and by flow cytometry (Figure 3B). We next tested AML patient samples in similar fashion and found that IFN-γ significantly increased CD38 expression in these cells as well (Figure 3C). Hence,

not only does IFN- $\gamma$  promote Fc $\gamma$ R expression and function in AML cells, it also increases the expression of a candidate antigen target for antibody therapy. Next, to test which concentration of IFN- $\gamma$  was required for this up-regulation of CD38, we treated AML patient apheresis samples overnight with 0-10 ng/ml IFN- $\gamma$  and measured CD38 via qPCR. Results showed that as little as 0.5 ng/ml was sufficient to elicit a significant increase in CD38.

[figure not shown]
**IV. IFN- $\gamma$ -mediated CD38 up-regulation requires activation of Jak/Stat, p38 and NF- $\kappa$ B.** In order to determine which downstream signaling pathways were required for the up-regulation of CD38 seen

[figure not shown]
with IFN- $\gamma$  treatment, we pre-treated AML patient apheresis samples with inhibitors for Erk, PI3K, p38 MAPK, Jak/STAT and NF- $\kappa$ B. Results showed that IFN- $\gamma$ -mediated up-regulation of CD38 was significantly stunted in cells treated with inhibitors for Jak/Stat, p38 and NF- $\kappa$ B (Figures 4A, B and C, respectively), but not with inhibitors of the PI3K and Erk pathways.

**V. *IFN- $\gamma$  enhances antibody-mediated fratricide in AML cells.*** Results have shown that IFN- $\gamma$  of AML cells could promote their shift toward an M1 phenotype, could enhance the expression and function of Fc $\gamma$ R, and could also increase the expression of an antigen target for antibody therapy. This led us to test whether IFN- $\gamma$  treatment could promote an antibody-mediated killing of AML cells by one another, a phenomenon termed fratricide. To test this we first examined whether IFN- $\gamma$ -treated and antibody-opsonized THP-1 cells could form conjugates between one another. For this THP-1 cells were primed overnight with 10 ng/ml IFN- $\gamma$ . Cells were then labeled with either PKH-67 (green) or Claret (red) dye (Sigma Aldrich). The green-labeled cells were then incubated on ice for 60 minutes with 10  $\mu$ g/ml anti-CD38, washed and mixed at a 1:1 ratio (red: green). Following 3 hour incubation at 37 °C, cells were washed, fixed in 4% paraformaldehyde and analyzed by fluorescence microscopy using a red/green dual-filter objective (Figure 5A). The number of antibody-dependent conjugates (Green-Red and Green-Green) and non-specific conjugates (red-red) was scored in a blinded fashion (Figure 5B). The results demonstrate that indeed THP-1 cells attach to one another in an antibody-dependent manner.

